7.2.3. Handling of Missing Data

For efficacy assessments, if the scheduled visits (eg, 9-month) are not performed, the unscheduled and/or discontinuation visits performed within a 3-month window will be grouped with the scheduled assessments. For patients impacted by the COVID-19 pandemic, efficacy visits delayed up to 6 months will be included in the analysis.

Sensitivity analyses for the primary efficacy endpoint of mNIS+7 and the key secondary endpoint of Norfolk QoL-DN total scores, including different methods for handling of the missing data, will be conducted to assess the robustness of the primary analysis results.

More details of missing data handling will be described in the SAP.

7.2.4. Baseline Evaluations

Demographics and other baseline characteristics, including disease-specific information, will be summarized descriptively.

7.2.5. Efficacy Analyses

This Phase 3 study will use the placebo arm of the APOLLO study as an external control. Patient-level data from this study will be compared with patient-level data from APOLLO for efficacy analyses. For the primary and secondary clinical efficacy endpoints, the ALN-TTRSC02 arm in this study will be compared to the placebo arm from the APOLLO study. For the secondary endpoint of TTR percent reduction, the ALN-TTRSC02 arm in this study will be compared to the patisiran arm in this study. The treatment comparison will be conducted at Month 9 and/or Month 18. The efficacy endpoints beyond 18 months will be summarized descriptively.

The patisiran arm in this study will mainly serve as a reference arm. For the clinical efficacy endpoints at Month 9 and Month 18, the patisiran arm will be summarized descriptively and the treatment difference between ALN-TTRSC02 and patisiran arm in this study will not be tested.

7.2.5.1. Primary Endpoint

The primary endpoint mNIS+7 will compare change in mNIS+7 from baseline at Month 9 between the ALN-TTRSC02 group in this study and the placebo group in the APOLLO study. The treatment effect will be estimated based on the least squares (LS) means using an analysis of

covariance (ANCOVA) model with baseline mNIS+7 score as a covariate and factors including treatment group (ALN-TTRSC02 vs placebo), genotype (V30M vs non-V30M) and age of disease onset (<50 vs ≥50 years old). The primary endpoint will be tested at a significance level of 0.05 and must be significant to declare a positive trial.

Primary endpoint data that are missing will be multiply imputed separately for each treatment group using a regression procedure based on baseline covariates. The details will be specified in the SAP.

The mNIS+7 score for the patisiran group in this study will be summarized descriptively.

7.2.5.2. Secondary Endpoints

For the secondary clinical efficacy endpoints, the treatment comparison will be made between the ALN-TTRSC02 group in this study and the placebo group in the APOLLO study at Month 9 or Month 18 as specified. For the TTR percent reduction endpoint, the ALN-TTRSC02 group will be compared with the patisiran group in this study. To control the overall type I error, the secondary endpoints will be tested in the following hierarchical order:

- Norfolk QoL-DN total score change from baseline at Month 9
- 10-MWT gait speed change from baseline at Month 9
- mNIS+7 change from baseline at Month 18
- Norfolk QoL-DN total score change from baseline at Month 18
- 10-MWT gait speed change from baseline at Month 18
- mBMI (BMI [kg/m²] multiplied by serum albumin level [g/L]) change from baseline at Month 18
- R-ODS change from baseline at Month 18
- TTR percent reduction through 18 months

For change in Norfolk QoL-DN total score and 10-MWT gait speed from baseline at Month 9, the analysis will be based on an ANCOVA model similar to the model described for the analysis of change in mNIS+7 from baseline at Month 9, while adjusting for baseline value of the endpoint being modeled and including baseline NIS score (<50 vs ≥50) as an additional factor in the model. For these 2 endpoints, data that are missing will be multiply imputed separately for each treatment group using a regression procedure based on baseline covariates. The details will be specified in the SAP.

For change from baseline at Month 18 analyses, the analysis will be based on a mixed-effects model for repeated measures (MMRM), adjusting for a covariate (baseline value for the endpoint being modeled), categorical factors (treatment group, visit [Month 9 vs Month 18], genotype, age of disease onset, baseline NIS score), and an interaction term (treatment group by visit). For mNIS+7, baseline NIS score will not be included in the model.

In the APOLLO study, mBMI was not assessed at Month 9 or Month 18. The average values of Day 189 and Day 357 will be derived as Month 9, and the Day 546 value will be substituted as Month 18.

The TTR percent reduction through Month 18 will be derived as the average trough TTR percent reduction from Month 6 to 18 which is the steady state period for both ALN-TTRSC02 and patisiran. A Hodges-Lehmann method stratified by previous TTR stabilizer use (yes vs no) will be used to estimate the 95% CI for the median difference between the ALN-TTRSC02 and patisiran groups in this study. Non-inferiority will be declared if the lower limit of the 95% CI for the treatment difference is greater than -10%. A sensitivity analysis will be conducted to compare the TTR percent reduction between the ALN-TTRSC02 group from this study and the pooled patisiran groups from this Phase 3 study and the APOLLO study.

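### Against the non-randomised APOLLO placebo arm, age at onset (all clinical models) and baseline NIS (all but mNIS+7) are adjusted only by a split at 50, which can leave part of an imbalance in the estimate

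*Protocol*

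**What the plan says.** All references are to the Amendment 4 text of the protocol.

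- **Control.** Section 7.2.5: "This Phase 3 study will use the placebo arm of the APOLLO study as an external control", and "Patient-level data from this study will be compared with patient-level data from APOLLO for efficacy analyses".
- **Primary model (mNIS+7, Month 9).** Section 7.2.5.1 specifies an analysis of "covariance (ANCOVA) model with baseline mNIS+7 score as a covariate and factors including treatment group", with the further factors "genotype (V30M vs non-V30M) and age of disease onset (<50 vs ≥50 years old". NIS is not in this model.
- **Month 9 Norfolk QoL-DN and 10-MWT.** Section 7.2.5.2 uses a similar model "while adjusting for baseline value of the endpoint being modeled" and "including baseline NIS score (<50 vs ≥50) as an additional factor in the model".
- **Month 18 models.** The same section lists "categorical factors (treatment group, visit [Month 9 vs Month 18], genotype, age of disease onset, baseline NIS score". The cut points are not repeated, and I read them as the same ones. It adds: "For mNIS+7, baseline NIS score will not be included in the model".

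So age at onset is a two-level factor in every clinical model. Baseline NIS is a two-level factor in the Norfolk QoL-DN, 10-MWT, mBMI and R-ODS models and is absent from both mNIS+7 models.

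**The concern.** Between randomised arms a coarse covariate costs only some precision. Here the control comes from another study, so whatever imbalance the model fails to remove stays in the estimated treatment effect.

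The NIS cut at 50 is a HELIOS-A randomisation stratum (Section 3.5). That stratum balances ALN-TTRSC02 against patisiran, a contrast that Section 7.2.5 does not test on clinical endpoints. Age at onset is not a stratum at all. The usual reason for carrying a stratum cut into the model therefore does not apply to the comparison being tested.

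The cut also discards information already collected. NIS is a 244-point score (Section 6.2.1.2), measured twice at baseline (Table 1 notes), with entry from 5 to 130 (Section 4.1). The NIS factor gives one value to patients at 5 and 49, and another to patients at 51 and 130. Age at onset has no continuous counterpart in any model.

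Baseline differences between the two studies are more than hypothetical. Section 1.2 of the Amendment 2 summary reports that 36 of 122 vutrisiran patients (29%) met the cardiac subpopulation criteria, against 90 of 148 APOLLO patisiran patients (60.8%). That concerns neither NIS nor onset age, and not the placebo arm, but it shows that the populations can differ despite enrolment monitoring.

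**Working it through.** **1. The plan's own figure.** Section 7.1 gives a placebo change of 15 ± 17 (mNIS+7) and 11.5 ± 19.2 (Norfolk QoL-DN). The assumed changes on drug are 0 and −4, so the planned differences are 15 and 11.5 + 4 = 15.5. With 160 × 3/4 = 120 treated patients, two-sided 0.05, and the APOLLO placebo n varied because the protocol does not give it:

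| Assumed placebo n | Power, mNIS+7 | Power, Norfolk QoL-DN |
|---|---|---|
| 20 | 95.5% | 91.7% |
| 30 | 99.1% | 97.7% |
| 50 | >99.9% | 99.8% |

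The stated >90% holds for any placebo n of 19 or more. The protocol gives no figure for residual imbalance.

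**2. Share of a mean shift left by one split.** For a normal covariate with a linear effect, a small shift between groups, and no other term that captures it:

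share left = 1 − φ(c)² / [p(1 − p)],

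where p is the fraction on one side of the cut, c the matching normal quantile and φ the normal density.

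- p = 0.5: φ² = 0.1592, and 1 − 0.1592/0.25 = **36.3%**
- p = 0.3: 1 − 0.1209/0.21 = **42.4%**
- p = 0.2: 1 − 0.0784/0.16 = **51.0%**

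A correctly specified continuous linear term leaves 0% of a linear effect.

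**3. Relaxing the assumptions.** The protocol gives neither the distribution of NIS or onset age nor their correlation with the endpoint baselines. Large-sample least squares under assumed shapes gives:

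| Assumed case | Share left |
|---|---|
| Lognormal, cut at 50 | 40–45% |
| Uniform, location shift | 51% |
| Onset age, single peak | 36–39% |
| NIS bounded 5–130, shape differs, cut at 50 | 28–31% |
| Onset age two-peaked (33 and 62), late share 50% vs 60% | 5–13% |
| Normal NIS split plus continuous endpoint baseline, correlation 0.3 / 0.5 / 0.7 / 0.9 | 35 / 32 / 26 / 14% |

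**4. Size in points.** Residual bias = share left × imbalance in SD × correlation with outcome × outcome SD. With 0.363, an imbalance of 0.25 SD and a correlation of 0.1 to 0.4 (both assumed):

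- mNIS+7: 0.363 × 0.25 × 0.1 × 17 = 0.15, up to 0.363 × 0.25 × 0.4 × 17 = **0.62**; 0.62/15 = 4%.
- Norfolk QoL-DN: 0.363 × 0.25 × 0.1 × 19.2 = 0.17, up to 0.363 × 0.25 × 0.4 × 19.2 = **0.70**; 0.70/15.5 = 4.5%.

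Doubling the imbalance to 0.5 SD gives at most 1.23 and 1.39 points.

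If both covariates shift the same way by 0.2 to 0.4 SD, each worth 3 to 5 outcome points per SD (assumed), the bias left is 0.363 × 2 × 0.2 × 3 = 0.4 to 0.363 × 2 × 0.4 × 5 = 1.5 points. A simulation of that setting (120 vs an assumed 77 patients, residual SD 18) gave 0.4 to 1.4 points with the splits. With continuous terms it gave −0.16 to +0.14, which is simulation noise.

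**The case against.** Much of the opposing case stands.

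- **Adjustment is not the only safeguard.** Section 3.1 has baseline characteristics monitored, with possible enrolment limits. Section 3.4 caps patients with NT-proBNP above 3000 ng/L at 15%. Section 1.5 uses the patisiran arm to help validate the external control. A reader might infer that covariate adjustment is the sole protection; these sections show otherwise.
- **The models are not blind within a category.** Every secondary model carries the endpoint's own continuous baseline, which may separate patients on the same side of the NIS cut. In the mNIS+7 models severity enters through continuous baseline mNIS+7, which shares the weakness and reflex components with NIS (Section 6.2.1.3). Only onset age remains there, alongside genotype.
- **The share is not universal.** A reader might infer that a third or more of any imbalance survives. Step 3 gives 5% to 32% in several plausible cases, and the protocol supplies no distribution with which to choose among them.
- **Zero bias with a continuous term is built into a linear effect.** Nothing in the protocol shows that onset age acts linearly; under a threshold pattern the split could do as well. This is a reason to keep the factors and add to them.
- **Imputation terms are not fixed here.** Sections 7.2.5.1 and 7.2.5.2 leave those details to the SAP, so the split cannot be criticised there.
- **Timing.** This text is dated February 2021, with control data complete and an open-label study under way. Changing a prespecified primary model then is more than an editorial matter.

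None of this removes the point itself. Onset age has no continuous term in any model, and the only sensitivity method that Section 7.2.3 names is missing-data handling.

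**Conclusion.** The plan adjusts for onset age in all clinical models, and for NIS in the non-mNIS+7 models, more coarsely than a non-randomised comparison warrants. About 36% or more of a mean shift stays uncorrected if the covariate is near normal, acts linearly and is not otherwise captured; less stays if any of these fails in the ways shown. On the assumed inputs the residual bias is about 0.15 to 0.7 points, and up to roughly 1.4 in the harsher scenarios, against planned differences of 15 and 15.5.

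A reader might infer that the primary result is at risk. The documents do not support that: the bias is a small fraction of the planned effect, power is far above 90% for any but a very small placebo arm, and an imbalance in the opposite direction would make the estimate conservative. The point concerns accuracy of the estimates. Section 7.1 states planned effects only for mNIS+7 and Norfolk QoL-DN, so the relative size for 10-MWT, mBMI and R-ODS cannot be judged from the protocol.

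**What to change.** In the Month 9 ANCOVA and Month 18 MMRM models of Sections 7.2.5.1 and 7.2.5.2, keep the <50/≥50 factors. Add age at onset and, where NIS is already used, baseline NIS as continuous covariates, either linear or with a 3-knot spline. If the primary model is already locked, prespecify the extended model as a supplementary analysis and report it beside the primary estimate.

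The cost is two to four degrees of freedom in the models with both covariates and one or two in the mNIS+7 models. No new data are needed.

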During the Follow-up Period, all patients on ALN-TTRSC02 will undergo safety assessments quarterly until serum TTR levels return to $\geq 80\%$ of baseline (for up to 1 year after the last dose of study drug), or until the patient starts a TTR lowering regimen as a part of clinical care, whichever comes first; all patients will be followed for a minimum of 3 months. Female patients of child-bearing potential who discontinue ALN-TTRSC02 will be followed until serum TTR levels return to $\geq 80\%$ of baseline.

Statistical Methods

A full statistical analysis plan (SAP) will be finalized prior to first patient dosed.

The primary endpoint mNIS+7 will compare change in mNIS+7 from baseline at Month 9 between the ALN-TTRSC02 group in this study and the placebo group in the APOLLO study. The treatment effect will be estimated based on the least squares (LS) means using an analysis of covariance (ANCOVA) model with baseline mNIS+7 score as a covariate and factors including treatment group (ALN-TTRSC02 vs placebo), genotype (V30M vs non-V30M) and age of disease onset (<50 vs ≥ 50 years old). The primary endpoint will be tested at a significance level of 0.05 and must be significant to declare a positive trial.

For the key secondary endpoints of change in Norfolk QoL-DN total score and 10-MWT gait speed from baseline at Month 9, the analysis will be based on an ANCOVA model similar to the model described for the analysis of change in mNIS+7 from baseline at Month 9, while adjusting for baseline value of the

endpoint being modeled and including baseline NIS score (<50 vs ≥ 50) as an additional factor in the model. For these 2 endpoints, data that are missing will be multiply imputed separately for each treatment group using a regression procedure based on baseline covariates.

For change from baseline at Month 18 analyses, the analysis will be based on a mixed-effects model for repeated measures (MMRM), adjusting for a covariate (baseline value for the endpoint being modeled), categorical factors (treatment group, visit [Month 9 vs Month 18], genotype, age of disease onset, baseline NIS score), and an interaction term (treatment group by visit). For mNIS+7, baseline NIS score will not be included in the model.

The primary endpoint for the patisiran group in this study will be summarized descriptively.

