
 • To characterize the pharmacodynamic (PD) effect of ALN-TTRSC02 and patisiran on serum TTR and vitamin A levels • To characterize plasma pharmacokinetics (PK) of ALN-TTRSC02 and patisiran • To assess presence of antidrug antibodies (ADA) to ALN-TTRSC02 and patisiran 	
 – Troponin I and T levels, New York Heart Association (NYHA) class; – Neurologic Impairment Score (NIS); – EuroQoL-5 Dimensions-5 Levels (EQ-5D-5L) questionnaire and the EuroQoL-Visual Analog Scale (EQ-VAS); – Familial Amyloidotic Polyneuropathy (FAP) stage and Polyneuropathy Disability (PND) score; – Karnofsky Performance Status (KPS) • Change from baseline in technetium scintigraphy cardiac parameters at Month 18 • Percent reduction in serum TTR and vitamin A levels over time • PK profile of ALN-TTRSC02 and patisiran • Incidence and titers of ADA to ALN-TTRSC02 and patisiran
Safety	

 • To determine the safety and tolerability of ALN-TTRSC02 in patients with hATTR amyloidosis 	
 • Frequency of adverse events (AE)

For submission of the marketing authorization to the European Union, formal hypothesis testing will be conducted at Month 18, with mNIS+7 compared to the placebo arm of the APOLLO study at Month 18 considered the primary endpoint. Details will be specified in the statistical analysis plan (SAP).

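### The Month 18 MMRM gives each baseline covariate one coefficient for both visits, so a baseline difference from the external APOLLO placebo arm may be incompletely adjusted at Month 18

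*Protocol*

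**What the plan says.** In Section 7.2.5.2 of the Amendment 4 protocol, five clinical endpoints are tested at Month 18: mNIS+7, Norfolk QoL-DN, 10-MWT gait speed, mBMI and R-ODS. One model is given for all of them: "For change from baseline at Month 18 analyses, the analysis will be based on a mixed-effects model for repeated measures (MMRM". It is described as "adjusting for a covariate (baseline value for the endpoint being modeled), categorical factors (treatment group, visit [Month 9 vs Month 18], genotype", and from genotype on the list reads "genotype, age of disease onset, baseline NIS score), and an interaction term (treatment group by visit". One exception is made: "For mNIS+7, baseline NIS score will not be included in the model". The Statistical Methods part of the synopsis gives the same model. Neither place leaves the choice of model terms to the SAP, although the multiple-imputation details in Sections 7.2.5.1 and 7.2.5.2 are left to it.

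On the comparator, Section 7.2.5 says: "Patient-level data from this study will be compared with patient-level data from APOLLO for efficacy analyses". On the weight of this analysis, Section 2 says that for the EU submission the formal testing is at Month 18, "with mNIS+7 compared to the placebo arm of the APOLLO study at Month 18 considered the primary endpoint".

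**The concern.** With treatment-by-visit as the only interaction, the model estimates a separate treatment difference at each visit but holds each covariate effect constant across visits. In a randomised comparison that mostly costs a little precision, because the expected baseline gap is zero. Here the vutrisiran and placebo patients come from different trials, and covariate adjustment is the main analytic protection against confounding. A shared slope is a weighted average of the two visit-specific slopes. If these differ, Month 18 is adjusted with the wrong slope, and the error is multiplied by whatever baseline gap exists.

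Both conditions are plausible, though neither is established. The Amendment 2 summary of changes (Section 1.2) reports 36/122 vutrisiran patients in the Cardiac Subpopulation, against 90/148 patisiran patients in APOLLO. That is neither the placebo arm nor an mNIS+7 difference, but it shows that the two trial populations were not alike in one respect. Section 1.1 of the same summary says that the APOLLO treatment differences widened from Month 9 to Month 18, largely because placebo patients continued to progress. When change accumulates, its link with baseline status may also change.

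What is at stake is the accuracy of the five Month 18 estimates, including the EU primary one. The Month 9 primary analysis is a single-visit ANCOVA with its own slope, so the problem does not arise there.

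**Working it through.** **The plan's own figure.** The only power statement (Section 7.1) concerns Month 9: more than 90% for mNIS+7 with a difference of 15 and SD 17. About 160 patients at 3:1 gives about 120 on vutrisiran. With 120 treated, the statement reproduces for any placebo group of 16 or more. The protocol gives no effect, SD or power for the Month 18 model, so the Month 18 inputs below are assumptions, shown as ranges.

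**Formula.** Let the true covariate slopes be b9 and b18, and let the gap be the vutrisiran baseline mean minus the placebo mean. With complete data, the shared slope is w9·b9 + (1 − w9)·b18, where

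w9 = (s18² − r·s9·s18) / (s9² + s18² − 2·r·s9·s18),

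with s9 and s18 the residual SDs and r their correlation. The Month 18 contrast subtracts shared slope × gap where it should subtract b18 × gap, so

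bias at Month 18 = w9 × (b18 − b9) × gap.

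For genotype or age of onset, the gap is a difference in proportions and the slope is the factor's coefficient.

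**Numbers for mNIS+7.** s9 = 17 is taken from the APOLLO placebo SD in Section 7.1. s18, r, the slope change and the gap are assumed. Example: s18 = 22, r = 0.7 gives w9 = (484 − 261.8) / (289 + 484 − 523.6) = 222.2 / 249.4 = 0.89. With a slope change of 0.10 and a gap of 10, the bias is 0.89 × 0.10 × 10 = 0.89 points.

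| s9 | s18 | r | w9 | Bias, slope change 0.10, gap 10 |
|---|---|---|---|---|
| 17 | 17 | 0.7 | 0.50 | 0.50 |
| 17 | 25 | 0.5 | 0.84 | 0.84 |
| 17 | 22 | 0.7 | 0.89 | 0.89 |
| 17 | 25 | 0.7 | 1.03 | 1.03 |
| 17 | 25 | 0.85 | 1.38 | 1.38 |

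Over slope changes of 0.05 to 0.15 and gaps of 5 to 15 points, the size runs from 0.50 × 0.05 × 5 = 0.1 to 1.38 × 0.15 × 15 = 3.1 points. When Month 18 varies more than Month 9, the shared slope is mainly the Month 9 slope, so most of the error falls on Month 18, the visit being tested.

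**Simulation check.** 2,000 replicates, complete data, 120 treated and 75 placebo, vutrisiran 10 points lower at baseline, slopes 0.05 and 0.15, SDs 17 and 22 in both groups, r = 0.7. The Month 18 bias was −0.71 with the shared slope and +0.16 with a baseline-by-visit term. The simulation standard error of each is about 3.2/√2000 = 0.07. The two models were fitted to the same data, so their difference is the cleaner check: −0.71 − 0.16 = −0.87, against −0.89 from the formula. With no gap and equal slopes the two models gave the same result. Interval coverage in the run with a gap was 0.951 with the shared slope and 0.957 with the added term, so the error there was too small to harm coverage visibly.

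**The case against.** The strongest reply is that the bias needs two things the protocol does not show: a baseline gap, and slopes that differ by visit. Section 3.1 provides for monitoring baseline characteristics and possibly limiting enrolment to keep the populations comparable, and Section 3.4 limits patients with NT-proBNP above 3000 ng/L to 15%. The sign is not known in advance. If vutrisiran patients start less impaired and the slope rises with time, the benefit is overstated; if they start more impaired, it is understated. The size is small against the 15-point Month 9 difference assumed in Section 7.1, and nothing here shows a conclusion changing. All of this stands, and it is why the point is worded as a possibility. It does not remove the point: enrolment limits are optional and do not guarantee balance, and the safeguard is cheap.

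A second reply is that Section 2 leaves details of the EU testing to the SAP. That is correct, and the SAP may add terms. But Section 7.2.5.2 is the only Month 18 model the protocol gives, and Section 7 asks the SAP to follow the protocol's principal features.

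A reader might go further and infer that the model imposes one residual covariance on two different trials, so that intervals are too narrow and the type I error is inflated, at Month 18 and in the Month 9 ANCOVA. The protocol does not support this. It states no covariance structure and no standard-error method, and these may properly be settled in the SAP. The placebo sample size and the vutrisiran SD are not given either, and the direction depends on them. With assumed SDs of 14 (vutrisiran) and 20 (placebo), pooling gives a standard error 0.92 times the true one with 75 placebo patients, 1.00 with 120, and 1.04 with 150.

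**Conclusion.** The point holds in a limited, conditional form. As written, the Month 18 model holds each covariate effect constant across visits, and against a non-randomised control this may leave part of a baseline difference unadjusted at Month 18. For mNIS+7 the residual bias is about 0.5 to 1.4 points for an assumed slope change of 0.10 and a gap of 10 points, or 0.1 to 3.1 points over the wider assumed range. Against the assumed 15-point Month 9 difference, 0.5 to 1.4 points is about 3% to 9% (0.5/15 and 1.4/15). The figures rest on assumed Month 18 SDs, correlations, slopes and gaps, on complete data, and on one covariate taken at a time. They do not transfer directly to the other four endpoints, which have other scales. It would go too far to say that imbalance is left in the Month 18 result, or that the mNIS+7 conclusion is in doubt.

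**What to change.** In Section 7.2.5.2 and in the synopsis, add baseline-by-visit, genotype-by-visit and age-of-onset-by-visit terms to the Month 18 MMRM. For the endpoints other than mNIS+7, also add NIS-by-visit. With two visits, this is three extra parameters for mNIS+7 and four for each of the others. No new data are needed. With complete data, the Month 18 contrast then equals that of a Month 18 ANCOVA with the same covariates, which also brings it into line with the Month 9 analysis. The cost is a change of wording and possibly slightly wider intervals. The SAP should carry the same list of terms.
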